Time for kidney transplants will vary significantly between those receiving a living donor transplant and those receiving a deceased donor transplant. Typically, living donor kidney transplants are performed within 90 days after approval of an acceptable living donor at each of the participating transplant centers. We will make every effort to complete the screening evaluations and schedule the baseline visit ≥30 days before the patient's living donor kidney transplant procedure to maximize the number of eligible, consented participants who receive at least one dose of the Gardasil® 9 HPV vaccine prior to the transplant. Study participants who are expected to receive a kidney transplant from a deceased donor will be selected based on their likelihood of receiving the transplant within 12 months of enrollment, and depending on when the transplant actually gets scheduled (unpredictable time frame, given the knowledge of availability of a donor kidney and transplant surgery is usually a matter of <24 hours), the participants may be able to receive one, two or all three doses of the HPV vaccine prior to transplant.

Over an 18-month period we expect that 180 kidney transplant candidates will be consented and pass the medical chart review and pre-transplant clinic evaluations; 120 will receive one or two doses of the Gardasil® 9 HPV vaccine prior to transplant; 96 women will complete the 12-month post-transplant follow-up visit and receive the booster vaccine dose; and 64 women who have received the first vaccine dose > 30 days before their transplant will complete all follow-up.

Although all eligible, consented kidney transplant candidates will receive their first vaccine dose, we expect that a substantial fraction (perhaps one-third) of these candidates may not receive a transplant within the study period, largely because the identified donor will not pass through all the transplant eligibility screening testing in case of living donor transplant recipients, or no matching kidney from deceased donors becomes available in case of participants on the deceased donor transplant waiting list. Therefore, to meet the sample size requirement (N=64) for analysis of our primary endpoint, we enroll a higher number of participants than our expected target, expecting losses to follow-up at several stages in the study enrollment and follow-up cascade.

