#### **Pre-Transplant Vaccine Visits 2 and 3**

These visits are optional, and should be guided by the timing of surgery and feasibility of additional study-related visits. Participants who do not have Pre-Transplant Vaccine Visits 1 and/or 2 will still receive the complete 3-dose series of the vaccine (the remaining vaccination(s) will occur post-transplant. See Appendix B for a detailed schedule). If the Pre-Transplant Vaccine Visits 1 and 2 occur, the following intervals must be used:

- Pre-Transplant Vaccine Visit 2 should occur ≥30 days after Pre-Transplant Vaccine Visit 1. If possible (but not required), Pre-Transplant Vaccine Visit 2 should occur at least 30 days prior to Transplant Surgery.
- Pre-Transplant Vaccine Visit 3 should occur ≥3 months after Pre-Transplant Vaccine Visit 2, and ≥5 months after Pre-Transplant Vaccine Visit 1. If possible (but not required), Pre-Transplant Vaccine Visit 3 should occur at least 30 days prior to Transplant Surgery.

The following procedures will be performed during these visits:

- 1) Review of medical and surgical history, medications, and laboratory test results
- 2) Symptom assessment and ECOG performance status
- 3) Physical exam including vital signs and measurement of weight
- 4) Gardasil® 9 will be administered to the participant.
- 5) Blood draw A 28 mL blood specimen will be collected from each participant.
- 6) Self-collection of cervical/vaginal and oral samples for HPV DNA detection.
- 7) Self-collection of urine for HPV DNA detection from participants who consent to collection of optional urine samples.
- 8) Collection of eyebrow hairs (collected by research staff) for future viral DNA testing from participants who consent to collection of optional samples for biobanking for future studies

- 9) Self-collection of male genital samples for future HPV DNA testing from participants who consent to collection of these optional samples for biobanking for future studies
- 10) Interviewer-administered follow-up questionnaire to obtain information about changes in exposures and behaviors between study visits (Appendix F)
- 11) Review of inclusion/exclusion criteria and study requirements

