#### 11.1 Adverse Events

#### 11.1.1 Reportable AEs

All AEs that occur after the informed consent is signed and baseline assessments are completed (including run-in) must be recorded on the AE CRF (paper and/or electronic) whether or not related to study agent.

For all unsolicited AEs not meeting the criteria for "Serious Adverse Events", the following caveats will apply:

- a. **AEs in the immediate (up to 14 days) post-vaccination periods:** All unsolicited AEs, including anticipated and unanticipated clinical events, clinically significant laboratory abnormalities, and vaccine-related injection site local reactions (e.g., pain, swelling, erythema, pruritus, induration, warmth, etc.) and vaccine-related systemic side-effects (e.g., headache, oral temperature ≥100 degrees F, nausea, fatigue, dizziness, allergic events, bronchospasm, etc.) will be collected for up to 14 days following vaccine administration (1st, 2nd, and 3rd dose) and reported on AE CRFs.
  - i. Note that clinically significant laboratory abnormalities that *pre-dated* vaccine administration and *remain unchanged* (as per the Site Principal Investigator's judgment) after vaccine-administration should not be reported as AEs

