## b. AEs outside of the immediate post-vaccination periods (i.e., beyond 14 days):

- i. Anticipated clinically significant laboratory abnormalities, that in the view of either the Site Principal Investigator or the Sponsor, are related to the underlying renal disease, transplant procedure, or post-transplant regimens will not be collected or reported. (\*exceptions below)
- ii. Anticipated adverse events, that in the view of either the Site Principal Investigator or the Sponsor, are related to the underlying renal disease, transplant procedure, or post-transplant regimens *will not* be collected or reported. (\*exceptions below)

iii. All other adverse events will be collected and reported on AE CRFs. In situations where multiple AEs relate to a single unifying diagnosis, only the main unifying diagnosis should be reported as an AE on AE CRFs.

Example: In case of pneumonia with leukocytosis and chest pain that only requires outpatient treatment; the diagnosis of pneumonia should be reported as an AE, but leukocytosis and chest pain should not be reported as AEs.

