### Exploratory Endpoints:

- 1) Descriptive statistics, such as probabilities and exact 95% confidence intervals, will be used to summarize probability of seroconversion at 12 months post-transplant for the following groups:
  - a) time elapsed between last vaccine dose and the transplant procedure, e.g. <3 months vs. >3 months. Different groupings will be considered based on observed (e.g. median) and clinical considerations. Time will be summarized using descriptive statistics, e.g. median, interquartile range, or range; groups defined by dosing and types of post-transplant immunosuppressant medications, as well as;
  - b) type of transplant surgery (living donor/deceased donor);
  - c) differences in Human Leukocyte Antigen (HLA) histocompatibility between donor and recipient:
  - d) differences by biological sex (i.e., male vs. female) of the transplant recipient.
- 2) Stability of HPV vaccine-type-specific geometric mean titers (GMT) at 6 and 12- months post-transplantation, and rise in HPV vaccine-type-specific GMT at the 13 month post-transplant visit.
  - a) Stability will be evaluated in relation to changes in the type-specific GMTs between the two post-transplant time points (6- and 12-months post-transplant) and reported as follows: (i) decrease: more than 2-fold decrease, (ii) stable: within 2-fold change, and (iii) increase: greater than 2-fold increase.
  - b) The magnitude of increase in type-specific GMTs at the 13-month post-transplant visit (i.e., 1 month after the booster dose) will be described in relation to the type-specific GMTs at the other post-transplant visits (6 and 12-months post -transplant). Patterns over time will also be explored using graphical techniques.
  - c) Stability, and post-booster dose increase in type-specific GMTs will also be described in relation to the number of vaccine doses (1, 2 or 3) received in the pre-transplant period.
- 3) Vaccine safety profile and allograft rejection/opportunistic infections will be summarized using descriptive statistics, stratified by number of vaccine doses and time between the last vaccine dose and the transplant procedure.
- 4) HPV detection in samples from the anogenital, and oral cavity specimens at baseline (prevaccination) and at 6- and 12-months post-vaccination, overall and by number of vaccine

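### Whether a non-serious, anticipated transplant-related AE is recorded depends on days since a dose, and the exploratory safety summary is stratified by variables tied to that rule

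*Combined protocol and SAP*

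**What the plan says.** Section 11.1.1 sets two collection rules for unsolicited AEs that are not serious.

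- **Item (a), up to day 14 after a dose.** All such AEs, anticipated or not, and clinically significant laboratory abnormalities "will be collected for up to 14 days following vaccine administration". This covers the first, second and third doses.
- **Item (b), beyond day 14.** Anticipated AEs and laboratory abnormalities that, in the view of the site principal investigator or the sponsor, "are related to the underlying renal disease, transplant procedure, or post-transplant regimens" are not collected. For the rest: "All other adverse events will be collected and reported on AE CRFs".

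The exceptions to (b) are rejection at any time and events that cancel a planned transplant; both are reported as SAEs. Section 11.2.2 collects all SAEs and hospitalizations except the planned transplant stay itself, plus AEs relevant to prolonging that stay. The introduction to Section 11 adds that data on post-transplant infections and rejection will be collected.

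Dose 1 must be at least 30 days before surgery (Section 5.1). For Doses 2 and 3 this interval is only a preference (Section 7.3, Pre-Transplant Vaccine Visits 2 and 3): "If possible (but not required), Pre-Transplant Vaccine Visit 3 should occur at least 30 days prior to Transplant Surgery". For deceased-donor transplants, Section 4.4 (Feasibility) calls the time frame unpredictable, "given the knowledge of availability of a donor kidney and transplant surgery is usually a matter of <24 hours". Participants with one or two pre-transplant doses complete the series from 12 months after transplant (Section 5.1, Table 2).

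Section 13.5, exploratory item 3, then summarises the safety profile, rejection and opportunistic infections "stratified by number of vaccine doses and time between the last vaccine dose and the transplant procedure".

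**The concern.** Time from last dose to surgery decides whether the first post-operative days fall under rule (a) or rule (b). Number of pre-transplant doses decides whether such an overlap is possible, and how many 14-day windows open after transplant. The same non-serious, anticipated surgical event is recorded if the last dose was 5 days before surgery and not recorded if it was 40 days before.

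Item 3 tabulates safety by these two variables, and nothing in Sections 13.5 to 13.7 allows for the switch in rules. A difference in recorded AEs between strata could then come from the collection rule rather than from the vaccine. How safety varies with the interval and the number of doses is what the stratification is meant to show.

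**Working it through.** The plan states no figure for this summary, so there is none to reproduce. The check applies the rule directly and then illustrates its size.

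**1. Post-operative days under rule (a).** With the last dose *d* days before surgery, full collection covers max(0, 14 − *d*) post-operative days: 14 at *d* = 0, 11 at 3, 7 at 7, 4 at 10, 1 at 13, and none from *d* = 14. Over *d* = 1 to 13 the mean is 7. Collection is therefore partial even with an overlap: 7 days is 7/14 = 50% of a 14-day perioperative period and 7/30 = 23% of a 30-day one.

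**2. Who can have an overlap.** Dose 1 is at least 30 days before surgery, so one-dose participants cannot. Two- and three-dose participants can.

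**3. How many (assumed inputs).** Take surgery uniform over days 30-365 (336 days) and everyone dosed on schedule, with Doses 2 and 3 at days 30 and 150, or at days 60 and 180. Each dose gives 13 overlap days.

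- Share with overlap: 26/336 = 0.077 under either schedule.
- Expected number: 0.077 × 24 = 1.9 to 0.077 × 28 = 2.2.
- Chance of none, treating participants as independent: (1 − 26/336)^24 = 0.14 and (1 − 26/336)^28 = 0.10.

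These schedules give nearly everyone a second dose before surgery. Section 13.1 expects 24-28 of 96 (25-29%) to have one. That figure sits awkwardly with Section 13.3, where 24-28 is the whole evaluable sample. Scaling by it gives 0.077 × 0.25 × 24 = 0.5 to 0.077 × 0.29 × 28 = 0.6 participants.

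**4. Effect on recorded counts at equal true risk.** Let *q* be the share of perioperative AEs that are non-serious, anticipated and transplant-attributed, and *s* the share of the perioperative period under rule (a). Neither is in the documents. The recorded ratio, overlap versus no overlap, is [1 − *q*(1 − *s*)]/(1 − *q*).

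| *q* (assumed) | *s* = 0.5 | *s* = 1 |
|---|---|---|
| 0.25 | 1.17 | 1.33 |
| 0.50 | 1.5 | 2.0 |
| 0.75 | 2.5 | 4.0 |

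A whole stratum is diluted. If a fraction *f* of the short-interval stratum has an overlap, the ratio becomes 1 + *f·s·q*/(1 − *q*). Section 13.5 gives under versus over 3 months as an example grouping for seroconversion, and none for safety. Borrowing that split, the step 3 schedules give *f* = 26/181 = 0.144 or 26/211 = 0.123. With *f* = 0.144 and *s* = 0.5, the ratio is 1.02, 1.07 and 1.22 for *q* = 0.25, 0.5 and 0.75. Over *f* = 0.05 to 0.33 it runs from about 1.01 to 1.5.

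**5. Direction by number of doses.** Post-transplant doses also open rule (a) windows: 2 × 14 = 28 days for one-dose participants, 14 for two-dose and none for three-dose. The pre-surgery overlap averages only 0.077 × 7 = 0.5 days per participant under step 3. Perioperative days may, however, carry far more events than days a year later. The two effects run in opposite directions, and the net sign cannot be determined from the documents.

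**The case against.** The summary is exploratory and descriptive, with no test or decision rule. Item 3 does not say that all-cause AEs per person will be tabulated. Attribution is required for every AE (Sections 11.1.2 and 11.1.4), so surgical events can be recognised. If the summary is the proportion with any AE, the distortion could be slight: Section 6.2 reports injection-site pain in 63-90% of vaccinees aged 16-26, so most participants might count in every stratum. Capture under rule (a) may also be incomplete. Two- and three-dose participants have no research activity on the day of surgery (Section 7.3.4), and post-dose contact is one call at 24-72 hours, with a day-7 call only if symptoms are reported.

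These points limit the size and make a minor change the right response. They do not remove the problem: item 3 is not limited to related events, and recorded attribution helps only if the analysis uses it.

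A reader might infer that perioperative AEs in general go uncollected when the last dose was more than 14 days before surgery. The documents do not support that. SAEs, rejection, AEs prolonging the transplant stay and all other AEs are collected regardless. A reader might also infer that the two- and three-dose strata must look worse. The later windows of one- and two-dose participants rule out that conclusion.

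**Conclusion.** The point holds for one class of events: non-serious, anticipated AEs and laboratory abnormalities attributed to renal disease, the transplant procedure or post-transplant regimens. Their recording depends on the two variables used to stratify item 3, so recorded counts can differ between strata at equal true risk. By interval, the pre-surgery overlap adds recorded events to the short-interval stratum. By number of doses, the direction is unclear.

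The size is unknown. Under the assumed schedules the pre-surgery overlap involves about zero to two of 24-28 participants, and the count ratios above rest on assumed values of *q*, *s* and *f*. It would be too strong to say that the summary will show vaccination close to transplant to be less safe; there may be no overlap at all. With strata this small, though, one or two participants with several recorded surgical events could shift a descriptive count, and the table would not reveal why.

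The rule creates no difference for rejection. Infections are less clear: Section 11 says the data will be collected, but infections are not among the listed exceptions to 11.1.1(b).

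**What to change.** In Section 13.5, exploratory item 3:

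1. Compare SAEs, rejection and protocol-collected infections between strata over all follow-up.
2. Summarise non-serious AEs in the 14 days after a dose per dose, with days at risk as denominator, separately for pre-transplant and post-transplant doses.
3. List non-serious AEs with onset on or after surgery but within 14 days of a pre-transplant dose separately, with attribution. Leave them and their days at risk out of the stratum comparison. A dose 5 days before surgery then contributes 5 days, and events in the remaining 9 go to the listing.
4. Reconcile the introduction to Section 11 with 11.1.1(b) on whether non-serious post-transplant infections are collected at all times.

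Restricting the whole safety profile to events before surgery would go too far. It would discard post-surgical SAEs that are collected equally in every stratum, and would leave the interval comparison with only events that precede the transplant.

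The cost is a few sentences. Dose, AE-onset and surgery dates are already captured, and dosing, visits and the 14-day collection rule do not change. The small downside is that a non-serious delayed vaccine reaction starting after surgery appears only in the listing.

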# 13.6 Reporting and Exclusions

We anticipate some drop-outs due to transplantation complications, health deterioration, or death. The drop-out rate is expected to be 20%, resulting in a final sample of 24-28 participants who complete the study.

#### 13.7 Evaluation of Toxicity

All participants will be evaluable for toxicity from the time of their first dose of the Gardasil® 9 nonavalent HPV vaccine.

# 13.8 Evaluation of Response

Vaccine serologic response will be evaluated for all participants who receive at least one dose of Gardasil® 9.

#### 13.9 Interim Analysis

There will be no planned interim analyses.

#### 13.10 Ancillary Studies

Not applicable.

#### 14. ETHICAL AND REGULATORY CONSIDERATIONS

#### 14.1 Form FDA 1572

Prior to initiating this study, the Protocol Lead Investigator at the Lead or Participating Organization(s) will provide a signed Form FDA 1572 stating that the study will be conducted in compliance with regulations for clinical investigations and listing the investigators, at each site that will participate in the protocol. All personnel directly involved in the performance of procedures required by the protocol and the collection of data should be listed on Form FDA 1572.

#### 14.2 Other Required Documents

- 14.2.1 Current (within two years of Drug Shipment Authorization) CV or biosketch for all study personnel listed on the Form FDA 1572 and Delegation of Tasks form for the Lead Organization and all Participating Organizations.
- 14.2.2 Current professional licensure (if applicable) for all study personnel listed on Form FDA 1572 and Delegation of Tasks form for the Lead Organization and all Participating Organizations.
- 14.2.3 Lab certification (e.g., CLIA, CAP) and lab normal ranges for all labs listed on Form FDA 1572 for the Lead Organization and all Participating Organizations.
- 14.2.4 Documentation of training in "Good Clinical Practice (GCP)" for all study personnel listed on the FDA Form 1572 and Delegation of Tasks form for the Lead Organization and all Participating Organizations.

- 14.2.5 Documentation of Federal Wide Assurance (FWA) number for the Lead Organization and all Participating Organizations.
- 14.2.6 Signed Investigator's Brochure/Package Insert acknowledgement form
- 14.2.7 Delegation of Tasks form for the Lead Organization and all Participating Organizations signed by the Principal Investigator for each site and initialed by all study personnel listed on the form
- 14.2.8 Signed and dated NCI, DCP Financial Disclosure Form for all study personnel listed on Form FDA 1572 for the Lead Organization and all Participating Organizations

# 14.3 Institutional Review Board Approval

Prior to initiating the study and receiving agent, the Investigators at the Lead Organization and the Participating Organization(s) must obtain written approval to conduct the study from the NCI Central IRB (CIRB). Should changes to the study become necessary, protocol amendments will be submitted to the DCP PIO according to DCP Amendment Guidelines. The DCP-approved amended protocol must be approved by the CIRB prior to implementation

#### 14.4 Informed Consent

All potential study participants will be given a copy of the CIRB-approved Informed Consent to review. The investigator will explain all aspects of the study in lay language and answer all questions regarding the study. If the participant decides to participate in the study, participants will be asked to sign and date the Informed Consent document. The study agent(s) will not be released to a participant who has not signed the Informed Consent document. Subjects who refuse to participate or who withdraw from the study will be treated without prejudice.

Participants will be provided the option to allow the use of blood samples, other body fluids, and tissues obtained during testing, operative procedures, or other standard medical practices for further research purposes. A statement of this option will be included within the informed consent document.

Prior to study initiation, the informed consent document must be reviewed and approved by NCI, DCP, the Consortium Lead Organization, NCI CIRB, and the IRB at each Organization at which the protocol will be implemented. Any subsequent changes to the informed consent must be approved by NCI, DCP, the Consortium Lead Organization's IRB, NCI CIRB, and then submitted to each organization's IRB for approval prior to initiation.

#### 14.5 Submission of Regulatory Documents

All regulatory documents are collected by the Consortia Lead Organization and reviewed for completeness and accuracy. Once the Consortia Lead Organization has received complete and accurate documents from a participating organization, the Consortium Lead Organization will forward the regulatory documents to DCP's Regulatory Contractor:

Paper Document/CD-ROM Submissions: Regulatory Affairs Department CCS Associates, Inc. [name] [name]

[contact]

[contact]

E-mail Submissions: [contact]

Regulatory documents that do not require an original signature may be sent electronically to the Consortium Lead Organization for review, which will then be electronically forwarded to DCP's Regulatory Contractor.

